## 10. MEASUREMENTS

### For clinicaltrials.gov and Stanford Clinical Trials Directory compliance

#### **Primary Outcome Measure**

**Title:** Percentage of patients that are able to complete 3 cycles of neoadjuvant therapy and undergo a curative surgical resection.

**Time Frame:** At time of surgery

**Safety Issue:** No

#### **10.1 Primary and Secondary Outcome measures**

The primary outcome measure for each patient is an indicator for successfully completing 3 cycles of neoadjuvant atezolizumab, followed by surgical resection of remaining disease. The treatment will be evaluated as non-feasible for patients who have disease progression during neoadjuvant treatment, discontinue study medications due to toxicity, or are not able to undergo curative surgical resection after the 3 cycles of treatment.

Patients who decline surgical intervention after completing the neoadjuvant treatment will be considered as having successfully received neoadjuvant treatment.

In this study, feasibility was chosen as the primary endpoint to assess whether patients can successfully complete the neoadjuvant treatment without significant disease progression precluding curative surgical resection, and with acceptable toxicity. Since the patient population will include tumors that are resectable at presentation (and patients will be medically fit to undergo surgery), any postponement of definitive surgical resection will need to demonstrate that this does not adversely affect the opportunity for curative therapy. If this postponement of surgery proves to not cause harm and administration of neoadjuvant treatment is feasible, this study may add an additional cohort to evaluate a combination of immune checkpoint inhibitors in this setting. Future studies can be designed that evaluate additional clinical endpoints.

##### **10.1.1 Relevant Subset**

All patients that receive at least 1 dose of Atezolizumab will be considered as “evaluable” patients for this feasibility study.

#### **10.2 Secondary Outcome**

The overall response rate and pathological response rate (complete and major pathological response) following completion of neoadjuvant therapy will be reported with a 95% exact confidence interval.

Objective response rate will be measured based on RECIST v1.1 criteria (Appendix F). Overall response rate will be determined based on Appendix F, Table 1. Pathological response will be assessed by local pathological review. Patients with no viable tumor seen will be classified as a complete pathological response. Patients with < 10% of viable tumor will be classified as a major pathological response.

The change in surgical margins, vital structures preserved, morbidity, and/or surgical approach will be described qualitatively for each patient in the study and summarized.

### **10.2.1 Relevant Subset**

The objective response rate will be evaluated for all patients that had both sets of imaging (pre-treatment and after cycle 2). All patients that had surgery will be included to assess pathological response rate, change in surgical margins, and vital structures preserved.

## **11. REGULATORY CONSIDERATIONS**

### **11.1 Institutional Review of Protocol**

The protocol, the proposed informed consent and all forms of participant information related to the study (e.g. advertisements used to recruit participants) will be reviewed and approved by the Stanford IRB and Stanford Cancer Institute Scientific Review Committee (SRC). Any changes made to the protocol will be submitted as a modification and will be approved by the IRB prior to implementation. The Protocol Director will disseminate the protocol amendment information to all participating investigators.

The Principal Investigator is responsible for keeping the IRB apprised of the progress of the study and of any changes made to the protocol as deemed appropriate, but in any case, the IRB must be updated at least once a year. The Principal Investigator must also keep the IRB informed of any significant AEs.

Investigators are required to promptly notify their respective IRB of all adverse drug reactions that are both serious and unexpected. This generally refers to SAEs that are not already identified in the Investigator's Brochure and that are considered possibly or probably related to the molecule or study drug by the investigator. The study team will immediately forward to their IRB any written safety report or update provided by Genentech (Investigator's Brochure, safety amendments and updates, etc.).

Atezolizumab is an FDA approved drug for various indications including non-small cell lung cancer, small cell lung cancer, and Alveolar Soft Part Sarcoma (ASPS). etc. Neither the investigator, nor the sponsor, Genentech, Inc. intend to report the study data to the FDA as a well-controlled study in support of a new indication or any other significant change in the labeling for Atezolizumab, nor do we intend, at this time, to utilize the study data to support a significant change in the advertising of atezolizumab. The drug is currently not approved for CSCC; however we believe this study is IND-exempt, for the risks are not expected to be beyond what is seen with the routine SOC use of this agent.

### **11.2 Data and Safety Monitoring Plan**

The Stanford Cancer Institute Data and Safety Monitoring Committee (DSMC) will be the monitoring entity for this study. The DSMC will audit study-related activities to determine whether the study has been conducted in accordance with the protocol, local

standard operating procedures, FDA regulations, and Good Clinical Practice (GCP). This may include review of the following types of documents participating in the study: regulatory binders, case report forms, eligibility checklists, and source documents. In addition, the DSMC will regularly review serious adverse events and protocol deviations associated with the research to ensure the protection of human subjects. Results of the DSMC audit will be communicated to the IRB and the appropriate regulatory authorities at the time of continuing review, or in an expedited fashion, as needed.

This clinical research study will be monitored both internally by the PI and externally by the Stanford University IRB. In terms of internal review, the PI will continuously monitor and tabulate AEs. Appropriate reporting to the Stanford University IRB will be made. The PI of this study will also continuously monitor the conduct, data, and safety of this study to ensure that:

Interim analyses occur as scheduled,  
Stopping rules for toxicity and/or response are met,  
Risk/benefit ratio is not altered to the detriment of the subjects,  
Appropriate internal monitoring of AEs and outcomes is done,  
Over-accrual does not occur,  
Under-accrual is addressed with appropriate amendments or actions, and  
Data are being appropriately collected in a reasonably timely manner.

### **11.3 Data Management Plan**

The Protocol Director, or his/her designee, will prepare and maintain adequate and accurate participant case histories with observations and data pertinent to the study. Study specific Case Report Forms (CRFs) will document treatment outcomes for data analysis and safety information including AE's, conmeds collected at the specified timepoints. Case report forms will be developed using the REDCap database system and will be maintained by the clinical trial coordinators. CRFs will be kept in a locked office, only accessible to the research team. The REDCap database for data management will be developed prior to enrollment. The database will be locked 3 months after the last patient visit per study calendar for the primary and secondary analyses.

The study coordinator and investigators are responsible for ensuring that the eligibility checklist is completed in a legible and timely manner for every patient enrolled in the study, and that data are recorded on the appropriate forms and in a timely manner. Any errors on source data should be lined through, but not obliterated, with the correction inserted, initialed, and dated by the study coordinator or PI. All source documents will be available for inspection by the FDA and the Stanford University IRB.

FDA regulations (21 CFR §312.62[c]) and the ICH Guideline for GCP (see Section 4.9 of the guideline) require that records and documents pertaining to the conduct of clinical trials and the distribution of investigational drug, patient records, consent forms, laboratory test results, and medication inventory records, must be retained for 2 years after the last marketing application approval in an ICH region or after at least 2 years have elapsed since formal discontinuation of clinical development of the investigational

product. All state and local laws for retention of records also apply.

#### **11.4 Compliance with Laws and Regulations**

Patients who comply with the requirements of the protocol, are tolerating study treatment, and may be receiving benefit will be offered dosing beyond Cycle 1 at the investigator's discretion after a careful assessment and thorough discussion of the potential risks and benefits of continued treatment with the patient. Such patients may have the option to receive MPDL3280A treatment as long as they continue to experience clinical benefit in the opinion of the investigator until the earlier of unacceptable toxicity, symptomatic deterioration attributed to disease progression, or any of the other reasons for treatment discontinuation listed in Section 4.8.

#### **11.5 Confidentiality**

Patient medical information obtained by this study is confidential and may be disclosed to third parties only as permitted by the ICF (or separate authorization to use and disclose personal health information) signed by the patient or unless permitted or required by law.

Medical information may be given to a patient's personal physician or other appropriate medical personnel responsible for the patient's welfare for treatment purposes.

Data generated by this study must be available for inspection upon request by representatives of the FDA and other regulatory agencies, national and local health authorities, Genentech representatives and collaborators, and the IRB/Ethics Committee (EC) for each study site, if appropriate.

### **12. STATISTICAL CONSIDERATIONS**

#### **12.1 Statistical Design**

The primary objective is to determine the feasibility of three doses of atezolizumab prior to surgery in patients with advanced cutaneous squamous cell carcinoma. Our baseline assumption is that 50% of the population will complete all 3 doses of atezolizumab and then proceed to surgery. We can prove that with 20 patients by showing that 85% of the patients enrolled will complete the 3 neoadjuvant cycles of PD-L1 and then proceed to surgery. We will also be collecting demographic and descriptive data on tumor characteristics, and therapies. Please refer to sections 12.4 to 12.7 for the study's statistical plan.

This approach will be considered feasible if 17 or more patients are able to complete neoadjuvant treatment and proceed with surgical resection of disease. If 4 or more patients are unable to complete neoadjuvant treatment due to toxicity or tumor progression, or have unresectable disease at the time of surgery, this approach will be considered unfeasible. Patients who decline immunotherapy or surgery due to reasons not related to toxicity or tumor progression, will not be considered a treatment failure.

## **12.2 Randomization**

Not applicable.

## **12.3 Interim analyses**

Accrual will be limited to no more than 6 patients at a given window of immunotherapy dosing and 10 days post recovery from surgery. Toxicity and treatment failures will be reviewed prior to each additional patient accrual. If the number of patients who fail neoadjuvant treatment exceeds the maximum number allowable to achieve the primary objective, the study will be stopped early (i.e. treatment failure in 4 patients).

## **12.4 Descriptive Statistics and Exploratory Data Analysis**

Baseline demographic data, tumor characteristics, staging information, and complete treatment data (including surgery and adjuvant therapies), will be recorded and presented at the completion of the trial.

## **12.5 Primary Analysis**

The evaluation of feasibility will be based on percentage of patients completing 3 cycles of neoadjuvant atezolizumab and followed by surgical resection of remaining disease. We expect 85% of patients will fall in feasibility category, leaving only 3 patients unable to complete 3 cycles and undergo surgery. With such a small subsample, instead of using quantitative analysis method, we will develop in-depth, detailed case study aiming to assess the potential differences between these cases and the rest of patients in potential confounders such as patients' demographics, comorbidities, tumor stage, and surgical morbidity.

The change in surgical plan will be recorded by the primary surgeon based on initial assessment of the tumor and the size and location of the tumor at the time of definitive surgical resection.

## **12.6 Secondary Analysis**

Objective response rate will be assessed per investigator assessment and pathological response rate will be assessed by local pathology review. The overall response rate and pathological response rate following completion of neoadjuvant therapy will be reported with a 95% exact confidence interval.

The change in surgical margins, vital structures preserved, morbidity, and/or surgical approach will be described qualitatively for each patient in the study and summarized. For objective response rate, we will look at the response assessment at each cycle for visible lesions and record the greatest dimension. For all lesions, we will also be using RECIST to assess tumor progression and record tumor size from the CT scan which will be done at baseline, and then after cycle 2. For lesions that are not visible, we will only assess response after cycle 2 when an interval set of imaging is performed.

The pathological response rate will be measured by pathologists at the local institution

and be recorded as a percentage of viable tumor remaining. Tumors with 0% viable tumor will be considered a complete pathological response, and tumors with >0% and  $\leq 10\%$  will be classified as a major pathological response. The change in surgical margins will be measured in 3 dimensions by the surgical investigator based on anticipated surgical resection at presentation, and again at the time of surgery. The number of vital structures preserved per patient will be recorded and include >50% of the nose, lip, ear, or eye. These data will be presented in a table format at the conclusion of the study.

## 12.7 Sample Size

### 12.7.1 Accrual estimates

Based on the number of patients seen at the Stanford Head & Neck Oncology Clinic there are about 2 patients seen per month who would qualify for this study. We estimate that 8 patients annually will be enrolled in the study, and will require 42 months to complete the study.

### 12.7.2 Sample size justification

The primary objective is to determine the feasibility of three doses of atezolizumab prior to surgery in patients with advanced cutaneous squamous cell carcinoma. The sample size of evaluable 20 patients allows at least 80% power to reject the null hypothesis of 50% if the true fraction is above 80% (or a difference  $>30\%$ ) using binomial enumeration of all possible outcomes, with a test at the 5% significance level. We expect the true fraction is 85%, which means that we are well powered to detect an effect size that is bigger than 30%.

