## 7.2 Safety Parameters and Definitions

Safety assessments will consist of monitoring and reporting adverse events and serious adverse events per protocol. This includes all events of death and any study-specific issue of concern.

The Stanford Cancer Institute Data and Safety Monitoring Committee (DSMC) will be the monitoring entity for this study. The DSMC will audit study-related activities to determine whether the study has been conducted in accordance with the protocol, local standard operating procedures, FDA regulations, and Good Clinical Practice (GCP). This may include review of the following types of documents participating in the study: regulatory binders, case report forms, eligibility checklists, and source documents. In addition, the DSMC will regularly review serious adverse events and protocol deviations associated with the research to ensure the protection of human subjects. Results of the DSMC audit will be communicated to the IRB and the appropriate regulatory authorities at the time of continuing review, or in an expedited fashion, as needed.

In addition to the DSMC above, no more than six patients at a time will be permitted to be dosed concurrently. More specifically, we will limit the accrual rate to this such that a maximum of 6 patients at any one time will be in the window between immunotherapy dosing and 10 days post recovery from definitive surgery. All patient safety data for this study will be reviewed by Drs. [name] and/or [name], and documented on the AE log. If there are any adverse events (Grade 3 or higher or serious of any grade) attributed to checkpoint inhibitor treatment, further enrollment to the study will be put on hold until the attribution is understood and the protocol has been modified accordingly (with IRB notification and approval) to mitigate the future risks to patients. Our statistical design was powered with the least number of patients necessary to achieve our primary objective. If during the course of the study, the number of patients who fail to complete the neoadjuvant protocol (due to drug related toxicity or tumor progression) is such that the primary objective would be unachievable, the study will be stopped early. Based on our statistical design, if at any point during the study, 4 patients fail to complete the neoadjuvant protocol, the study will be stopped early.

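### The 80% power in section 12.7.2 belongs to a 15-of-20 cut; the 17-of-20 rule that decides the trial has 41% power at a true 80% and 65% at the expected 85%

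*Combined protocol and SAP*

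**What the plan says.** Section 12.7.2 (Sample size justification) sets a null rate of 50%, a 5% significance level and exact binomial enumeration. It states that the design "allows at least 80% power to reject the null hypothesis of 50% if the true fraction is above 80" per cent. It then gives 85% as the expected true rate and calls the study well powered. It gives no critical value and does not say whether the test is one- or two-sided.

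The decision rule is in section 12.1 (Statistical Design): "This approach will be considered feasible if 17 or more patients are able to complete neoadjuvant treatment and proceed with surgical resection of disease". The same section declares the approach unfeasible at 4 or more failures, and describes the aim against a 50% baseline as "We can prove that with 20 patients by showing that 85% of the patients enrolled will complete the 3 neoadjuvant cycles".

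Two other sections carry the same count:

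- Section 7.2: "if at any point during the study, 4 patients fail to complete the neoadjuvant protocol, the study will be stopped early". It presents this as following from the statistical design and adds: "Our statistical design was powered with the least number of patients necessary to achieve our primary objective".
- Section 12.3 stops the study if the number of failures "exceeds the maximum number allowable to achieve the primary objective, the study will be stopped early (i.e. treatment failure in 4 patients").

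Section 12.5 (Primary Analysis) states no decision rule and no hypothesis test. Its expectation of 85%, "leaving only 3 patients unable to complete 3 cycles and undergo surgery", is numerically the 17-of-20 boundary.

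**The concern.** A power statement describes a particular rejection rule. Section 12.7.2 describes a test of 50% at the 5% level, but no section uses that test to reach the trial's conclusion. The conclusion comes from 17 successes or 4 failures, which is a much stricter bar.

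The figure of 85% also has two roles. In section 12.1 it is the proportion that must be observed (17/20); in section 12.7.2 it is the expected true rate. A bar set at the expected value will be missed by chance a good part of the time.

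At stake is the false-negative risk on the primary endpoint. Section 12.8 makes the larger trial depend on meeting this endpoint. A reader of sections 7.2 and 12.7.2 would conclude that a regimen with a true completion rate of 80% or more has at least an 80% chance of passing.

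**Working it through.** **Inputs.** n = 20 evaluable patients, null rate 50%, exact test at 5%, alternative 80% and expected rate 85% (all section 12.7.2). Feasible at 17 or more successes (12.1). Stop at the 4th failure (7.2, 12.3). Assumption for the main figures: each of the 20 patients is either a success or a failure, so X ~ Binomial(20, p).

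**Step 1: reproduce the plan's figure.** Find the smallest r with P(X ≥ r | p = 0.50) ≤ 0.05.

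- r = 14: 0.0577, which fails.
- r = 15: 0.0207 one-sided, 2 × 0.0207 = 0.0414 two-sided, which passes.

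The upper critical value is 15 on either sidedness. Power is P(X ≥ 15 | 0.80) = 0.804 and P(X ≥ 15 | 0.85) = 0.933. So "The sample size of evaluable 20 patients allows at least 80% power" is correct arithmetic for a 15-of-20 cut.

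**Step 2: the rule that decides.** P(X ≥ 17 | p) = Σ C(20,k) p^k (1−p)^(20−k), for k = 17 to 20.

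- p = 0.50: 0.00109 + 0.00018 + 0.00002 + 0.00000 = 0.0013
- p = 0.80: 0.2054 + 0.1369 + 0.0576 + 0.0115 = 0.411
- p = 0.85: 0.2428 + 0.2293 + 0.1368 + 0.0388 = 0.648

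| True rate | P(≥15 of 20), implied by 12.7.2 | P(≥17 of 20), rule in 12.1 | P(≥4 failures) |
|---|---|---|---|
| 50% | 0.0207 | 0.0013 | 0.999 |
| 80% | 0.804 | 0.411 | 0.589 |
| 85% | 0.933 | 0.648 | 0.352 |
| 90% | 0.989 | 0.867 | 0.133 |

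Solving P(X ≥ 17 | p) = 0.80 gives p = 0.883.

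**Step 3: effect of the early stop.** Under the success-or-failure assumption, 4 or more failures in 20 is exactly X ≤ 16, the complement of 17 or more successes. Stopping at the 4th failure therefore changes when the study ends, not the probabilities above.

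**Step 4: where the two rules disagree.** With 15 or 16 successes the test in 12.7.2 rejects 50%, but the rule in 12.1 declares the approach unfeasible. The probability is 0.804 − 0.411 = 0.393 at a true 80%, and 0.933 − 0.648 = 0.285 at 85%.

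**Step 5: decliners.** Section 10.1 counts patients who decline surgery after completing neoadjuvant treatment as successes. Section 12.1 does not count unrelated decliners as failures. The documents give no decline rate, so 5% to 10% (1 to 2 of 20) is assumed here.

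- Decliners count as successes, success probability d + (1−d)p: with d = 0.05 and 0.10, power is 0.456 and 0.503 at a true 80%, and 0.684 and 0.719 at 85%.
- Decliners count as neither and 17 successes are still required, so P(X ≥ 17) with n = 19 or 18: power is 0.237 and 0.099 at 80%, and 0.441 and 0.224 at 85%.

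No reading reaches 80% power at either rate.

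**Step 6: precision at the boundary.** The exact (Clopper–Pearson) 95% confidence interval for 17/20 is 62.1% to 96.8%.

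**The case against.** The best defence is that section 12.7.2 contains no arithmetic error. It claims power to reject 50%, and that claim is true of the exact 5% test. A significance test and a stricter go/no-go bar can coexist. The written bar also errs on the cautious side: its type I error is 0.13%, a pass leads only to the design of a larger trial, and this is a single-arm feasibility study. That the calculation itself is right must be granted. The defect is that the plan never says the powered test and the deciding rule differ, and section 7.2 tells the reader that the design was powered for the primary objective, which is decided at 17 of 20.

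A second objection is that 41% and 65% rest on counting every patient as a success or a failure, which sections 10.1 and 12.1 do not strictly do. This is a fair caveat. If some decliners fall in neither category, 4 failures and fewer than 17 successes also cease to be complements. But the range in the working moves the figures without bringing any of them to 80%.

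Third, the sections do not agree in every detail. Section 12.5 states no rule, and section 7.2 describes failure as drug-related toxicity or progression, while section 12.1 adds unresectable disease at surgery. That is correct, but sections 7.2, 12.1 and 12.3 all give the count of 4, and section 12.7.2 is the only place with a power claim that does not fit it.

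**Conclusion.** The concern holds. The power in section 12.7.2 is not a property of the rule that decides this trial. With every patient counted as a success or a failure, the stated power exceeds that of the 17-of-20 rule by 39 percentage points at a true 80% (80.4% against 41.1%) and by 28.5 points at 85% (93.3% against 64.8%). If the true rate is the expected 85%, the study ends as unfeasible 35% of the time; at 80%, 59% of the time. Counting an assumed 5% to 10% of decliners as successes raises power to no more than 50% at 80% and 72% at 85%. Counting them as neither lowers it. The correction is needed because the plan's only statement of power misdescribes the primary decision.

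**What to change.** Keep 20 evaluable patients, the 17-of-20 rule and the stop at 4 failures, and make the text describe them.

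1. In section 12.7.2, remove the claim of at least 80% power above 80% and the statement that the study is well powered. Replace them with, for example:

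> With 20 evaluable patients and the rule in section 12.1, each patient being counted as a success or a failure, the probability of declaring feasibility is 0.1% if the true rate is 50%, 41% at 80%, 65% at 85% and 87% at 90%.

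2. Next to this, state how decliners enter the count, so that the assumption behind these figures matches sections 10.1 and 12.1.
3. In section 12.5, add that the primary proportion will be reported with an exact 95% confidence interval. Section 12.6 already does this for the response rates.
4. As a follow-on edit, bring the sentence in section 7.2 about the design being powered, and the claim of proof in section 12.1, into line with the new text.

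It may be noted, as description only, that 17 of 20 corresponds to a one-sided exact 5% test of a rate of about 65% (P(X ≥ 17 | 0.65) = 0.044). The documents do not justify 65% as a benchmark, and it should not be presented as one.

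If the sponsor instead intends the test of 50% with 80% power to decide the trial, sections 7.2, 12.1, 12.3 and 12.7.2 contradict one another and must be reconciled. No stopping count is proposed here.

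The cost is rewording. No patients are added, and the stated power becomes less favourable.
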